10.2 Unanticipated Problems

10.2.1 Adverse Events

AEs will be noted on CRFs similar to those used in the study of buprenorphine-naloxone treatment for opioid addicted youth ([name] et al, 2008). Medical staff will evaluate the intensity, seriousness, and causal relationship of the AE to study medication and procedures. The PI, Project Director, and NET@PPS or NET Steps medical staff will ask participant what adverse events have occurred since the last visit. Medical Staff will judge “possibly” or “definitely” related to the study, and record the event in the AE CRF. A report describing it will be sent to the Penn and Prison IRBs within the defined reporting period unless otherwise defined as serious. Then it must be reported in 5 days and followed up to determine its outcome. Unanticipated problems involving risk to subjects or others will be reported for any incident, experience, or outcome that meets any of the following criteria: 1) Unexpected in nature, severity or frequency (i.e., not described in study-related documents such as the IRB-approved protocol or consent form, product information, etc.); 2) Related or possibly related to research participation (i.e., a reasonable possibility that the experience or outcome may have been caused by procedures involved in the research); 3) Suggests that the research places subjects or others at risk of physical, psychological, economic, or social harm.

10.2.2 Definition of Adverse Event (AE): These are defined as any symptom, sign, illness, or experience that develops or worsens during the course of the study. Abnormal results of diagnostic procedures are considered AEs if they result in study withdrawal, are associated with a serious adverse event, lead to additional treatment or further diagnostic tests, and/or are considered by the investigator to be of clinical significance.

10.2.3 Recording Adverse Events:

At each patient contact the research team will seek information on AEs by specific questioning and, as appropriate, by examination. Information on all AEs will be recorded in the source document and also on the appropriate CRF. All clearly related signs, symptoms, and abnormal diagnostic procedures or results should be in the source document. The clinical course of each event should be followed until resolution, stabilization, or until it has been determined that study treatment or participation is not the cause. SAEs that are ongoing at the end of the study must be followed up to determine the final outcome. Any SAE that occurs after the study and is considered possibly related to the treatment or study participation should be recorded and reported immediately.

10.2.4 Unanticipated Problems for Immediate Reporting of an AE(s):

- 1) Any AE that, even without detailed analysis, represents a SAE that is rare in the absence of drug exposure (i.e. agranulocytosis, hepatic necrosis, Stevens-Johnson syndrome).
- (2) Any AE that would cause a change in the product information, protocol or informed consent, or would prompt IRB action to assure protection of human subjects.

10.2.5 AE Relationship to Study Intervention

Consider date and time of on-set, severity, and relatedness to known side effects.

10.3 Serious Adverse Events

10.3.1 Characteristics of a Serious Adverse Event

An SAE is an AE that is fatal, life threatening, requires or prolongs a hospital stay, results in persistent or significant disability or incapacity, a congenital anomaly or birth defect, or an important unanticipated medical event. Such events may not be life threatening but may jeopardize the subject or require intervention to prevent a serious outcome. For example, drug overdose, a seizure that did not result in inpatient hospitalization, or intensive treatment of bronchospasm in an emergency department would be considered serious.

10.3.2 Reporting SAEs: Disability, hospitalization or prolongation of hospitalization, congenital defects, and life-threatening events are SAEs that must be reported (orally, e-mail, fax) to the Penn and Prison IRBs at the time they are identified if they are judged related or possibly related to the study, or unexpected. A written report is to be filed within 5 working days to these IRBs and the sponsor. When additional clinical information is available, a follow-up and/or final SAE report is to be filed. If the report is supplied as a narrative, the minimum necessary information at the time of the initial report includes: study identifier, subject number, description of event, date of onset, current status, if study treatment was discontinued, reason why event was considered serious, and whether it was related to study treatment or procedures. Copies of each report and documentation of IRB notification and receipt will be kept in the study file.

10.3.3 Reporting Deaths: The Penn IRB requires that investigators report a death within 24 hours when it is unexpected and indicates participants or others are at increased risk of harm. Other deaths are to be reported within 72 hours, regardless of whether they were related to study participation.

10.4 Adverse Event Reporting Period: The period during which AEs must be reported begins at study initiation, including assessment of any preexisting conditions and ends at the last follow-up.

10.6.3 Unanticipated Problems Reporting to IRB

- (1) Change in FDA safety labeling or withdrawal from marketing of a drug, device, or biologic used in a research protocol.
- (2) Breach of confidentiality
- (3) Change to the protocol without prior IRB review in order to eliminate apparent immediate hazards.
- (4) The research team cannot resolve a complaint that indicates unexpected risks.
- (5) Protocol violation (an accidental or unintentional deviation from the approved protocol) that in the opinion of the investigator placed one or more participants at increased risk or affects the rights or welfare of subjects.

10.7 Women and the Reporting of Pregnancies

Pregnancy is an exclusion criterion for entry into the study. Women who test positive during the pregnancy test at screening will not be permitted to be in the study. Pregnancy tests will be repeated monthly prior to XR-NTX injections for females who have not relapsed.

Lactating females must agree not to breast feed. Sexually active females of child-bearing potential (i.e., women who are not menopausal or who have not had a bilateral oophorectomy, hysterectomy, or tubal ligation) must agree to use one of the following methods of birth control from the date they sign the ICF until 24 hours after their final dose of study drug:

- a. Hormonal contraception (i.e., oral contraceptive, contraceptive implant, or injectable hormonal contraceptive)
- b. Double-barrier birth control (e.g., condom plus intrauterine device, diaphragm plus spermicide, etc.)
- c. Maintenance of a monogamous relationship with a male partner who has been surgically sterilized by vasectomy.

Patients who become pregnant during the study will not be eligible for continuing extended-release naltrexone since it is not approved for use during pregnancy, but delivery will be followed up to determine if there was any evidence of fetal harm or an abnormality. These patients will be referred to other treatments. The investigator must notify the IRB and study sponsor of patients who become pregnant during the study as an adverse event (AE).

11. PATIENT REMUNERATION:

Patients will receive \$100 cash dispersed through the use of a Greenphire ClinCard , or equivalent voucher at a local retail outlet for months 1, 3, and 6 for the time they spend doing these monthly assessments. Patients can

receive an additional \$30.00 on their Greenphire ClinCard for coming in for their first scheduled visit in Week 1 as scheduled by the study staff. Patients will receive \$20.00 for their month 2, 4 and 5 visits which are briefer. Participants will also receive \$15.00 for travel and time for weekly visits not including the monthly visits at weeks 1 -3, 5 -7, 9 – 11, 13 – 15, 17 – 19, and 21 – 23. Estimated costs for travel expenses are in the budget justification.

Travel Costs: Many inmates lose public assistance and welfare benefits upon incarceration and typically have no legal income, no medical benefits, and no medical transportation benefits after re-entry. The Patient Benefits Managers will seek and secure benefits for subjects that lost them, a process that currently averages 6 weeks post re-entry but will be shortened by starting it before reentry. The maximum amount of reimbursement they can receive if they keep all assessment appointments is \$660.

12. CLINICAL MONITORING

The Study Coordinator will monitor the sites on a weekly basis to review logs and procedures. The Quality Assurance Monitor will visit the sites on a monthly basis to review source documents and procedures, and she will visit the study offices weekly to monitor regulatory requirements.

13 STATISTICAL HYPOTHESES AND PLAN

13.1 Primary Aims

Before performing analyses, we will apply the following data screening and cleaning procedures: 1) screen for data-entry errors; 2) check for outliers; 3) assess the extent and pattern of missing data, and 4) check that appropriate assumptions of normality are met, as necessary. In all analyses, we will examine whether the assumptions underlying the application of statistical methods have been met, principally through use of standardized residuals, influence diagnostics, and graphical displays. We will check to confirm that the groups do not differ on baseline relevant background variables using analyses of variance (ANOVA) for continuous variables and log-linear models for binary or ordinal responses. The randomization process should minimize the need for inclusion of covariates to reduce bias in treatment comparisons. However, we will consider relevant covariates for inclusion in analyses to improve precision of estimation of treatment effects (Hauck et al. 1998). The statistical procedures that will be used to examine each outcome are listed below.

13.2 Primary Aim 1—Proportion Without Relapse by Month 3:

At each monthly assessment we will determine whether a subject has relapsed based on self-report, physical examination, response to a naloxone challenge, or information from program staff of significant others. Using these data, we will create a binary outcome reflecting whether or not the participant relapsed during the 3 months post-release. We will compare the proportion of participants who relapsed in the two groups using a logistic regression analysis. The analysis will include group as a predictor variable along with all relevant covariates (including the stratification variables). Relapsed will be defined by self-report of 10 or more days in the past 30 days or by two or more opiate positive urine samples in the last 30 days. Positive urine samples will be computed as 5 days of opioid use for each sample. The analysis will be performed using SAS's PROC LOGISTIC.

13.3 Power Analyses for Primary Aim:

There are relatively few data to estimate power for this study since so little work has been done in this area. We know that most relapses from various substance dependencies occur in the first 3-6 months ([name] & Cacciola, 1994). For opioid addiction it typically occurs in the first days or weeks (Binswanger et al, 2007) and for opioid addicted prisoners, often on the way home from jail, according to reports from the two Recovery Specialists and

more than half of the focus group participants. We also know that XR-NTX will prevent relapse for a month and that more than twice as many prisoners that did not receive it before reentry relapsed by the second month after reentry as compared with those that received it before reentry (Lee et al, 2013). Regarding the issue of how long patients will continue on XR-NTX, 79% of the XR-NTX patients in the O'Brien et al study received their first 3 injections and 73% received their first 4. In the Krupitsky et al study (2011) 78% received their first 3 injections and 70% received their first 4 (data provided by [name], Alkermes, 2014).

The Lee et al study most closely resembles the one proposed here, however our study has a stronger control group than Lee et al because patients in our control group will be offered XR-NTX at NET Steps after reentry and all participants will have a Patient Benefits Manager to help reinstate benefits that were lost while incarcerated. Putting these data together, we estimate a 23-33% group difference in relapse rates by month 3. Power estimates calculated using this estimate and following the recommendations of Cohen with a 2-sided alpha of .05 and a baseline sample size of 100 per group result in 80% power to detect a difference in relapse rates of approximately 20% (OR = 2.4) between the two groups assuming a relapse rate of 50% in the control condition and 10% and 20% attrition by the 3- and 6-month follow-ups. These outcomes are clinically meaningful based on the severe consequences from untreated opioid addiction, the evidence that continuing in treatment reduces them, and confirmation of their importance by conversations with ex-prisoners and the Recovery Specialists, and focus group participants.

13.4 Secondary Aims:

- 1) Quality of life;
- 2) Weeks in treatment through month six;
- 3) Time to relapse;
- 4) Rearrests;
- 5) Psychiatric symptoms;
- 6) Opioid use;
- 7) Alcohol and other drug use;
- 8) HIV risk;
- 9) Reincarceration;
- 10) Deaths.

We will use linear mixed effects models (Littell, Milliken, Stroup, & Wolfinger, 1996) to examine group differences on continuous longitudinal outcomes (i.e., 1) quality of life scores, 5) Psychiatric symptoms, 8) HIV risk scores,) and non-linear mixed effects models (Diggle, Heagerty, Liang, and Zeger, 2002) to compare the groups on binary longitudinal outcomes (i.e., 6) opioid, 7) alcohol, and other drug use). Mixed effects models have advantages over conventional repeated measures methods as they allow for missing observations, provide greater flexibility in modeling the variance-covariance matrix, and permit the estimation of both group and random subject-specific effects. Models will be calculated using SAS's PROC GLIMMIX and MIXED, respectively. We will use a Poisson regression model to compare the groups on 2) weeks in treatment through month 6. We will use a Cox proportional hazards regression model to determine whether the time to relapse (3) differs across the two groups. The analysis will account for the fact that the data will likely be right-censored as some participants may experience a relapse during the period of observation. The analysis will include relevant covariates and will be performed using SAS's PHREG. The models will include a terms for group, time, and their interaction as well as any necessary covariates. Finally, we will use logistic regression to compare the two groups on binary cross sectional outcomes (i.e., 4) rearrest, 10) death, and 9) reincarceration). The models will be similar to that described for the primary outcome.

13.5 Missing values:

Missing data will not be an issue for several of the outcomes (i.e., days in treatment, re-arrest, re-incarceration). The most important source of missing data is likely to be dropout. As recommended by Lavori (1992), we will analyze the data under an intent-to-treat principle, in which all participants initially randomized will be included. Logistic regression models predicting dropout, based on patient characteristics and prior measures, will be used to determine whether the dropout process is ignorable (i.e. whether missed visits are well explained by observable data). Although these models provide a formal framework for assessing sensitivity to missing data, much of their implementation proceeds in an exploratory manner.

13.6 Maintenance of Data on Retention Efforts:

To assist in follow-up we will utilize “Participantfile”, a computerized record of participant information. This software was designed and programmed by our research team over the past 10 years and was used in the CTN “STRIDE” study of exercise for stimulant dependence. It provides secure, immediate access to a variety of follow-up information on each patient. All contact information will be included in this database including: names, phone numbers and addresses of friends or relatives who might know where the patient can be located, aliases and “nicknames,” hangouts, other study subjects known, and treatment programs. Access to these encrypted data is strictly controlled through a database security system. The database will be stored on a removable disk that will be locked in a safe storage area at the end of each day. All attempts to locate subjects will be recorded in Participant file. This allows staff to know the status of any missed patient so others can assist in follow-up work if necessary. It also allows supervisors, the site PI, or project manager to monitor workloads, schedule calls, personalize letters, etc. For example, if all calls are unanswered in the morning, calls at another time are indicated. Leads will continue to be recorded and discussed at weekly staff meetings.

14 Training Plans

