3.1 Study Outcome Measures

3.1.1 Primary

Proportion not relapsed by month three.

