8) Naloxone challenge: A baseline COWS is administered prior to the naloxone challenge by administering 0.4 to 0.8 mg of naloxone I.M. and observing the patient for 15 - 30 minutes to establish absence of physiological dependence (score of <5 on the COWS). A second COWS is administered after the naloxone challenge is given and the patient is also observed for 15 – 30 minutes. The naloxone challenge is done prior to subsequent XR-NTX doses unless it is clear that there has been no relapse, or that relapse has occurred, in which case it will not be done. Determination presence/absence of relapse is a clinical evaluation based on self-report, urine test results, reports from significant others (if available), and physical examination (rhinorrhea, lacrimation, fresh tracks or puncture marks). If withdrawal occurs after a naloxone challenge, clonidine 0.2 to 0.6 mg will be administered to suppress it and the participant will be observed with blood pressure checks every 15 minutes until symptoms subside and there is no evidence of clonidine-induced hypotension.

9) Relapse to Opioid Dependence with Physiological Features: Determined from self-report, physical assessment, urine tests, reports from significant others if available, and/or a positive naloxone challenge in cases where it is administered prior to a XR-NTX.

10) Time to Relapse: Determined by time between absence of physiologic dependence and time that relapse occurred, and documented using methods described above.

11) Weeks in Addiction Treatment: Data obtained from NET Steps clinical records, patient self-report, and verification from other treatment provider (for those reporting treatment elsewhere). A week will be counted as beginning on Monday and ending the following Sunday. Having 5 or more days of protected time from a previous XR-NTX injection, or receiving 5 or more days of methadone or buprenorphine-naloxone, or having a counseling appointment lasting 30 minutes or more will be counted as a week in treatment.

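### Section 13.2's relapse count rule is not expressly given precedence over 5.5 and 8.1 item 9, and the first-dose test schedule can give Group B extra scored urines inside the post-release window

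*Combined protocol and SAP*

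**What the plan says.** **Section 13.2.** The outcome is "a binary outcome reflecting whether or not the participant relapsed during the 3 months post-release". Two descriptions of relapse follow in one paragraph:
- A source list: "we will determine whether a subject has relapsed based on self-report, physical examination, response to a naloxone challenge, or information from program staff" or significant others. It has no threshold and does not mention urine.
- A count rule, applied to a 30-day look-back: relapse is "defined by self-report of 10 or more days in the past 30 days or by two or more opiate positive urine samples". A conversion is attached: "Positive urine samples will be computed as 5 days of opioid use for each sample". The Relapse CRF (8.1 item 28) repeats the conversion. Neither place says whether these days are added to self-reported days.

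**Section 3.1.1.** The endpoint is only "Proportion not relapsed by month three", with no reference to release.

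**Section 8.1.** Item 9 reads "Relapse to Opioid Dependence with Physiological Features: Determined from self-report, physical assessment, urine tests", then adds informants and the naloxone challenge; no count is given. Item 10, time to relapse, is "Determined by time between absence of physiologic dependence and time that relapse occurred", a start that is not tied to release.

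**Section 5.5.** After a positive first-dose urine the participant is retested three days later, and not producing a negative result then is counted as relapse. The rule is worded for both groups. Group A's first-dose test is scheduled before re-entry. Group B's is after release, within 7 days in 5.5, while 5.1 allows the first dose up to 30 days after release.

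**Urine schedule.** Weekly urines are listed from Week 2 for both arms (7.3). The Week 1 urine sits under Baseline/Enrollment (7.2). Section 8.1 item 6 and the visit payments in section 11 refer to week 1 without saying whether Group A gives a urine in its first week after release.

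**The concern.** The primary endpoint turns on counting positive urines, and two are enough. A rule that adds a sample after a positive result, or a first-week sample that only one arm supplies, raises the chance of reaching two whatever the participant's true use. If those samples fall inside the scoring window in one arm only, the arms are measured with different intensity. As scheduled that arm is Group B, so the distortion would favour XR-NTX before reentry.

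Separately, two analysts could score the same data differently, depending on whether they apply the count rule alone, add the 5.5 relapses, or accept clinical determinations under item 9. The trial is not double blinded (16.2), so it is better to settle this before the data are examined.

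**Working it through.** **1. The plan's power figure.** Inputs from 13.3: 100 per group, 10% attrition by month 3 (n = 90), control relapse 50%, two-sided alpha 0.05. A pooled two-proportion test gives 78.7% for 50% v 30%, and 81.1% for 50% v 29.4% (OR 2.4, since 1/(1 + 2.4) = 0.294). The stated 80% reproduces and is not in question. It supplies the yardstick of about 20 points.

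**2. First-dose results under each rule.**

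| Result | 5.5 | 13.2 count rule |
|---|---|---|
| Positive, then positive | relapse | relapse (2 urines) |
| Positive, repeat missed | relapse, if a missed test counts as failure | not relapse (1 urine) |
| Positive, then negative | not relapse | not relapse |

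The two rules themselves differ only in the second row. In the first row they agree, but the second urine exists only because of the repeat.

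**3. Position against the post-release window, as scheduled.**

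| Sample | Group A | Group B |
|---|---|---|
| First-dose urine | before release, outside | after release, inside |
| 3-day repeat | before release, outside | after release, inside |
| Weekly urines from Week 2 | inside | inside |
| Separate post-release week-1 urine | not established | first-dose urine can fill this slot |

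Group B's possible extra samples are therefore the repeat and, if Group A has no post-release week-1 urine, the first-dose urine itself.

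**4. Exceptions to that schedule.** No text requires Group A's test to be at least 3 days before release, so its repeat can fall after release. Monthly windows are ±1 week, so if visits run from release a month-1 visit can fall at day 21 to 28. A 30-day look-back then reaches 21 − 30 = −9 to 28 − 30 = −2, that is, 2 to 9 days before release. Held-over Group A participants have their schedule reset, under rules that differ between 5.1 and 5.5.

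**5. Size, by simulation.** The documents give no rate of positive first-dose tests, so every behavioural input is assumed. The model has two-state daily use, the same in both arms, and honest self-report. First-dose testing is on day 3 or 7 (also day 1 or 5 in the calibrated runs). Urines follow on days 14, 21, … 84, with 30-day look-backs at days 30, 60 and 90. The excess is Group B minus Group A in scored relapse, in percentage points.
- *Repeat only, steady use:* 0.1 to 3.4. Calibrated to the plan's 50% relapse rate, 0.7 to 3.4, or 1.2 to 4.2 if 30% of repeats are missed and read as relapse.
- *First-dose urine only, with no matching urine in Group A:* 0.0 to 4.6.
- *Both, steady use:* about 0 to 7. The two maxima come from different settings, so the total stays below 4.6 + 3.4 = 8.0.
- *Repeat only, early use* (0.3 per day, ending between day 3 and day 21, relapse about 50%): 1.7 to 11.6, depending strongly on the assumed pattern.
- *Group A pre-release double positives also scored* (repeat only, three steady settings): +0.9 to −1.3 at 5% daily in-custody use, and −0.5 to −3.6 at 10%.

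**6. Effect on the test.** With n = 90 per group, no true difference and x added to Group B, the two-sided rejection probability is 1 − Φ((c − x)/s₁) + Φ((−c − x)/s₁). Here c = 1.96·√(2p̄(1 − p̄)/n), and s₁ is the unpooled standard error. For base 50% and x = 0.05, c = 0.146 and s₁ = 0.0744, giving 10.3%. Over base rates of 30% and 50%, x = 2, 5 and 10 points give about 6%, 10–11% and 27–29%. These values of x are assumed.

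**7. Adding urine days.** Enumerating 0–30 reported days by 0–4 positive urines, the rules [days ≥ 10 or urines ≥ 2] and [days + 5 × urines ≥ 10] differ only for one positive urine with 5, 6, 7, 8 or 9 reported days. In simulated steady-use settings with 48–61% relapse, the additive reading raises scored relapse within an arm by 9 to 27 points.

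**The case against.** **The count rule already governs.** Section 13.2 is the analysis section, its wording is definitional, and the Relapse CRF uses the same conversion. This largely stands: it is the natural reading. But 5.5 is just as categorical about what counts as relapse, and no sentence sets it aside for scoring.

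**Clinical judgement decides the endpoint.** A reader might infer this from 8.1 item 8 ("Determination presence/absence of relapse is a clinical evaluation based on self-report, urine test results"). In context that sentence only decides whether a naloxone challenge is given, so it does not support the inference. Item 9 is the genuine unthresholded description, and even it may be read as a list of inputs.

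**Extra relapses can arise only in Group B.** A reader might infer this from the schedule. It is too strong, because of the exceptions in step 4 of the working and because 3.1.1 does not exclude pre-release results. Group B participants who never attend also give no first-dose urine, which lowers ascertainment in that arm and is not modelled.

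**Early Group B positives are a real effect of delayed dosing.** Some will be, so the rejection rates above are illustrations and do not estimate bias. The concern is limited to differences in the number of samples scored.

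**Dropping the repeat is enough.** It is not. If Group A has no post-release week-1 urine, 0.0 to 4.6 points of Group B excess remain after the repeat is removed.

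**Conclusion.** The point holds as a should-fix matter of endpoint specification. The plan has one thresholded definition and competing statements that are not expressly subordinated to it. Its first-dose schedule can also place extra scored urines in Group B under the post-release window. With identical behaviour this can raise scored relapse in Group B by about 0 to 7 points under assumed steady use, and by more if use is concentrated early. Those figures rest wholly on assumed behaviour, and testing later than day 7, which 5.1 permits, was not modelled.

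The direction is conditional. It favours XR-NTX before reentry only if Group A's pre-release results are unscored and its repeats do not fall after release. A reader might go further and infer that the primary comparison is biased by a known amount, or that the power calculation is wrong. The documents support neither.

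**What to change.** For endpoint scoring only, with clinical handling unchanged:
1. State in 13.2 that the count rule is the single primary definition and overrides 5.5 and 8.1 item 9 for scoring.
2. Start the window at release in both arms, for the primary endpoint and for time to relapse (8.1 item 10). Exclude both pre-release urines and pre-release self-reported days from the 30-day look-back.
3. Score only urines from weekly post-release slots that exist in both arms, at most one per week. Count Group B's first-dose urine only as that week's sample, and only if Group A has a post-release urine in the same week; otherwise leave that slot out in both arms. Do not count the 3-day repeat as an additional sample, or a missed repeat as relapse.
4. State whether the 5 days per positive urine are added to self-reported days, and run the other reading as a sensitivity analysis. Add a further sensitivity analysis that includes 5.5 and clinically determined relapses.

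The Group B first-dose windows in 5.1 and 5.5, and the rules in those sections for held-over Group A participants, contradict each other and must be reconciled.

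The cost is wording in 13.2 and 8.1 items 9, 10 and 28, plus one scoring sentence for 5.5. No new data are needed. The downside is slightly fewer scored relapses, because valid positive repeats leave the primary count; the sensitivity analysis retains them.

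### Section 13.4 pairs the wrong SAS procedure with the binary drug-use outcomes and names no estimation method; GLIMMIX at its default would shrink the group odds ratio toward 1

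*Combined protocol and SAP*

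**What the plan says.** Section 13.4 (Secondary Aims) describes two families of longitudinal model. The first is for continuous outcomes (quality of life, psychiatric symptoms, HIV risk): "We will use linear mixed effects models". The second is non-linear mixed models, used "to compare the groups on binary longitudinal outcomes (i.e., 6) opioid, 7) alcohol, and other drug use". The software sentence follows and assigns the models to "PROC GLIMMIX and MIXED, respectively".

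The section prefers mixed models "as they allow for missing observations", because they "provide greater flexibility in modeling the variance-covariance matrix", and because they "permit the estimation of both group and random subject-specific effects". On fixed effects it says: "The models will include a terms for group, time, and their interaction as well as any necessary covariates".

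For the binary models it gives no estimation method, random-effect structure, variance or effect size. It also does not say which series is the outcome. Section 7.3 schedules urine screens weekly, and section 8.1 (item 7) collects self-reported use by Time Line Follow-Back at each monthly assessment. Either could supply it.

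**The concern.** Two things are wrong with the software sentence.

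- **The pairing.** Matched in order, GLIMMIX goes to the continuous models and MIXED to the binary ones. GLIMMIX can fit a normal outcome, so the first half does no harm. MIXED cannot fit the non-linear model that the section specifies for yes/no outcomes.
- **The estimation method.** Once the pairing is put right, the binary models run in GLIMMIX. With random effects and no METHOD option, GLIMMIX uses residual pseudo-likelihood. This is a fact about the software, not something the protocol states. The method linearises the model and fits a weighted linear mixed model repeatedly. With binary data and strong within-person correlation it underestimates the random-effect variance and the subject-specific log odds ratio.

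At stake are the reported odds ratios and intervals for two of the ten listed secondary outcomes: opioid use, and alcohol and other drug use.

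**Working it through.** **The plan's own figure.** Section 13.3 gives power for the primary aim only: 80% for about a 20-point difference (OR 2.4) from a 50% control relapse rate, 100 per group, 10% attrition by month 3. With 90 per group, 50% vs 30% gives 78.7%. With 50% vs 29.4% (OR 2.4: 1/3.4 = 0.294) it gives 81.1%. The figure reproduces, but it does not bear on this point beyond supplying a reference odds ratio. The documents give no bias, coverage or power figure for the drug-use models.

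**Inputs from the documents.** 100 per group (13.3); 20% attrition by month 6 (13.3); group, time and their interaction as fixed effects (13.4); about 24 weekly urine results (7.3) or about 6 monthly self-reports (8.1).

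**Assumed inputs.** A random intercept on the logit scale with SD 1 to 3, which is an intraclass correlation SD²/(SD² + 3.29) of 0.23 to 0.73. A subject-specific OR of 2.4, so a true log OR of -ln 2.4 = -0.875. Section 13.3 gives 2.4 for relapse, not for these outcomes.

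**Pseudo-likelihood** (REML on the linearised data, scale 1; 1,000 simulated trials per row):

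| Series | SD | Bias in log OR | Coverage | Empirical SD | Mean SE |
|---|---|---|---|---|---|
| 24 weekly | 1.0 | -5.5% | 94.2% | 0.149 | 0.152 |
| | 1.5 | -8.2% | 94.2% | 0.209 | 0.212 |
| | 2.0 | -12.0% | 91.9% | 0.280 | 0.268 |
| | 2.5 | -14.5% | 93.7% | 0.321 | 0.321 |
| | 3.0 | -17.7% | 91.9% | 0.377 | 0.366 |
| 6 monthly | 1.0 | -11.2% | 90.9% | 0.185 | 0.180 |
| | 1.5 | -17.5% | 88.3% | 0.225 | 0.221 |
| | 2.0 | -22.5% | 88.8% | 0.256 | 0.260 |
| | 2.5 | -29.0% | 86.7% | 0.299 | 0.295 |
| | 3.0 | -35.4% | 84.5% | 0.311 | 0.325 |

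A true OR of 2.4 would on average be reported as exp(0.875 × 0.945) = 2.29 (weekly, SD 1) to exp(0.875 × 0.646) = 1.76 (monthly, SD 3). A separately coded run at the same OR and SD range gave 5-18% with coverage 92-96% (weekly) and 11-31% with coverage 86-90% (monthly).

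**Width or centre?** Mean SE tracks the empirical SD throughout, so width is about right. A shift alone reproduces the coverage loss. For monthly data at SD 3:

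- shift: 0.354 × 0.875 = 0.310
- half-width: 1.96 × 0.325 = 0.637
- predicted coverage: Φ((0.637 - 0.310)/0.311) - Φ((-0.637 - 0.310)/0.311) = 85.2%, against 84.5% simulated

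At SD 1 the same sum gives 90.8%, against 90.9%.

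**Sensitivity to the effect.** Over SD 1 to 2, monthly coverage was 93-95% at OR 1.5 and 80-89% at OR 3.4. At a true log OR of -1 (OR 2.7), one further monthly run without the interaction term reached 37% attenuation and 78% coverage at SD 3. With no true effect there was no bias, and rejection was 4.3-6.0% across both series.

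**Dropout.** At a true log OR of -1, weekly data and SD 1.5, 2 and 3, bias was -8%, -11% and -19% under random 20% dropout. It was -9%, -13% and -21% when dropout depended on the last result. In another run at SD 2 the mean estimate was -0.90 with no dropout and -0.88 with outcome-dependent dropout.

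**Does quadrature repair it?** Same 200 trials, monthly, OR 2.4, SD 1.0 / 1.5 / 2.0:

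- pseudo-likelihood: bias -14% / -17% / -26%, coverage 85.5% / 89% / 86.5%
- adaptive quadrature: bias -3% / +1% / -2%, coverage 90.5% / 93% / 95%

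Monte Carlo error on coverage is 1.5-2 points. The SD 1.0 batch looks low for both methods, since pseudo-likelihood gave 90.9% there in the larger run. For weekly data at a true log OR of -1 (90 per arm, 330 trials), quadrature gave -0.99, -1.03 and -1.00 with coverage of 94%, 95% and 96% at SD 1.5, 2 and 3.

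**The case against.** The strongest reply is that the plan has not chosen pseudo-likelihood. It is silent on the method, the default comes from the software manual, and an analyst could select quadrature without departing from the text. The reversed order is an obvious slip that any SAS programmer would correct. The outcomes are secondary with no power target, the bias is toward no difference, and the primary analysis is an ordinary logistic regression (section 13.2).

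Much of this stands, and it is why the point is minor. It does not remove the point: the sentence has to be edited anyway, and naming a procedure without a method leaves the weaker method as what runs unless someone intervenes.

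A reader might also infer more than the documents support:

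- **One fixed bias and coverage figure for this trial.** Both depend on the SD, the effect and the series, none of which the documents give. At OR 2.4, weekly data with SD 1 to 1.5 lose under 10%.
- **Intervals that are too narrow.** Standard errors match the sampling variation; the intervals are centred in the wrong place.
- **A bias caused by informative dropout, undermining the missing-data reason for mixed models.** Nearly all of the shrinkage is present with complete data.
- **An invalid test.** Rejection under no effect stays close to 5%.

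**Conclusion.** The point holds as a minor correction to section 13.4. Read literally, the software sentence gives the binary outcomes a procedure that cannot fit the stated model. Read as evidently intended, it leaves GLIMMIX at a default that understates the subject-specific group effect.

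At a true OR of about 2.4 and a random-intercept SD of 1 to 3, the log odds ratio is attenuated by about 5-20% with 24 weekly results (coverage about 91-96%) and by about 11-35% with 6 monthly results (coverage about 85-91%). Smaller effects cost less coverage and larger ones more. The OR, the SD and the random-intercept structure are assumptions. The harm is limited to the estimates and intervals for the drug-use outcomes.

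**What to change.** In section 13.4:

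1. Correct the pairing: PROC MIXED for the continuous longitudinal outcomes, PROC GLIMMIX for the binary ones.
2. For the binary longitudinal outcomes, specify a subject random intercept fitted by METHOD=QUAD (adaptive quadrature), or METHOD=LAPLACE if several random effects are used.
3. State which series each model analyses: weekly urine results or monthly self-report.

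The cost is a sentence or two in the plan, one program option and slightly longer run time. Residual-side covariance structures are not available with quadrature, so within-person correlation has to be carried by the random effects. No new data are needed.
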